14.3 Interpreting Adverse Event Causality

The following factors should be considered when deciding if there is a "reasonable possibility" that an adverse event may have been caused by the study medication.

- Time Course. Exposure to suspect study medication. Has the subject actually received the suspect study medication? Did the adverse event occur in a reasonable temporal relationship to the administration of the suspect study medication?
- Consistency with known study medication profile. Was the adverse event consistent with the previous knowledge of the suspect study medication (pharmacology and toxicology) or drugs of the same pharmacological class? OR Could the adverse event be anticipated from its pharmacological properties?
- Dechallenge experience. Did the adverse event resolve or improve on stopping or reducing the dose of the suspect study medication?
- No alternative cause. The adverse event cannot be reasonably explained by another etiology such as the underlying disease, other drugs, other host or environmental factors
- Rechallenge experience. Did the adverse event reoccur if the suspected study medication was reintroduced after having been stopped Laboratory tests. A specific laboratory investigation (if performed) has confirmed the relationship?

A "reasonable possibility" could be considered to exist for an adverse event where one or more of these factors exist.

In contrast, there would not be a "reasonable possibility" of causality if none of the above criteria apply or where there is evidence of exposure and a reasonable time course, but any dechallenge (if performed) is negative or ambiguous or there is another more likely cause of the adverse events.

In difficult cases, other factors could be considered such as:

- Is this a recognized feature of overdose of the study medication?
- Is there a known mechanism?

Ambiguous cases should be considered as being a "reasonable possibility" of a causal relationship unless further evidence becomes available to refute this. Causal relationship in cases where the disease under study has deteriorated due to lack of effect should be classified as no reasonable possibility.

Verona Pharma plc CONFIDENTIAL Page 66 of 66

	2.1.8. RPL554 steady state pharmacokinetics (AUC _{0-12h} , Cmax, time to maximum co	
7)	31	

Document: Z:\ RPL554\UYA25849\Biostatistics\Documentation\SAP\Verona RPL554-CO-204 SAP v1.0

Author: [name] Version Number: 1.0

Version Date: [18OCT2018]

Template No.: CS_TP_BS016 Revision 5 Reference: CS_WI_BS005

Effective Date: 01Apr2018

17. REFERENCES	41
APPENDIX 1. PROGRAMMING CONVENTIONS FOR OUTPUTS	42
IQVIA Output Conventions	42
Table and Listing Output Conventions	42
Figure Output Conventions	44
Dates & Times	44
Spelling Format	45
Presentation of Treatment Groups	45
Presentation of Treatment Sequences	45
Presentation of Visits	46
Listings	46
APPENDIX 2. PARTIAL DATE CONVENTIONS	46
Algorithm for Treatment Emergence of Adverse Events	47
Algorithm for Prior / Concomitant Medications	48

Document: Z:\ RPL554\UYA25849\Biostatistics\Documentation\SAP\Verona RPL554-CO-204 SAP v1.0

Author: [name] Version Number: 1.0

Version Date: [18OCT2018]

Template No.: CS_TP_BS016 Revision 5 Reference: CS_WI_BS005

Effective Date: 01Apr2018

Page 9 of 50

1. Introduction

This document describes the rules and conventions to be used in the presentation and analysis of efficacy and safety data for protocol RPL554-CO-204. It describes the data to be summarized and analyzed, including specifics of the statistical analyses to be performed. The statistical analysis plan (SAP) is based on the final protocol version 2.0, dated 10JUL2018.

2. STUDY OBJECTIVES

2.1. PRIMARY OBJECTIVE

The primary objective of this study is to investigate the bronchodilator effect on peak forced expiratory volume in 1 second (FEV₁) (measured in the first 4 hours after dosing) of nebulized RPL554 dosed twice daily for 3 days, as compared to placebo, when administered in addition to once daily tiotropium/olodaterol. The peak FEV₁ is measured after the morning dose on Day 3.

2.2. SECONDARY OBJECTIVES

The secondary objectives are as follows:

- To assess the bronchodilator effect on peak FEV₁ (measured in the first 4 hours after dosing) and average (measured as the area under the curve [AUC]) FEV₁ over 12 hours of nebulized RPL554 after the first dose (on Day 1) as compared to placebo, when administered in addition to tiotropium/olodaterol
- To investigate the effect of twice daily nebulized doses of RPL554, as compared to placebo, when administered in addition to tiotropium/olodaterol on morning trough FEV₁ (mean of values 11 and 12 hours after last dose of RPL554) on Day 4
- To investigate the effect of twice daily nebulized doses of RPL554, as compared to placebo, when administered

Document: Z:\RPL554\UYA25849\Biostatistics\Documentation\SAP\Verona RPL554-CO-204 SAP v1.0

Author: [name] Version Number: 1.0

Version Date: [18OCT2018]

Template No.: CS_TP_BS016 Revision 5 Reference: CS_WI_BS005

Effective Date: 01Apr2018

Page 10 of 50

in addition to tiotropium/olodaterol on average (measured as AUC) FEV₁ over 4, 8 and 12 hours after morning dosing on Day 3

- To assess the bronchodilator effect on peak FEV₁ measured within 4 hours after the evening dosing of RPL554 on Day 3
- To analyze plasma concentrations and assess the steady state pharmacokinetics (PK) of RPL554 when administered in addition to tiotropium/olodaterol
- To assess the tolerability and safety of twice daily nebulized doses of RPL554 in addition to tiotropium/olodaterol
- To determine the onset of action of RPL554 when administered with tiotropium/olodaterol (after the first dose)
- To investigate the effects of RPL554 on specific airway conductance (sG_{aw}) and lung volumes (residual volume [RV], functional residual capacity [FRC]) when administered in addition to tiotropium/olodaterol

2.3. EXPLORATORY OBJECTIVES

The exploratory objectives are as follows:

- To assess the dose response of RPL554 on peak and average (measured as AUC over 12 hours) after morning dose on Day 3, and morning trough FEV₁ (mean of values at 11 and 12 hours after last dose of RPL554) on Day 4, when dosed in addition to tiotropium/olodaterol
- To examine the effect of RPL554 on top of tiotropium/olodaterol on average (measured as AUC) FEV₁ over 24 hours after 3 days of dosing
- To examine the effect of RPL554 on top of tiotropium/olodaterol on a Likert dyspnea scale

3. STUDY DESIGN

3.1. GENERAL DESCRIPTION

This is a Phase II, randomized, double blind, placebo controlled, complete block three-way crossover study to

Document: Z:\RPL554\UYA25849\Biostatistics\Documentation\SAP\Verona RPL554-CO-204 SAP v1.0

Author: [name] Version Number: 1.0

Version Date: [18OCT2018]

Template No.: CS_TP_BS016 Revision 5 Reference: CS_WI_BS005

Effective Date: 01Apr2018

Page 11 of 50

investigate treatment with nebulized RPL554 and tiotropium/olodaterol Respirat® in patients with moderate to severe chronic obstructive pulmonary disease (COPD).

A total of approximately 70 male or female COPD patients (as defined by the American Thoracic Society [ATS]/European Respiratory Society [ERS] guidelines with symptoms compatible with COPD for at least 1 year prior to Screening) aged 40 to 80 years (inclusive) will be randomized across up to 4 sites, in the Unites States (US) and the United Kingdom (UK). All patients will receive 3 combinations of study treatment (1.5 mg RPL554, 6 mg RPL554 and placebo) in a randomized, crossover design; therefore, each patient will act as his or her own control in the study. There are 6 possible treatment sequences a patient can be randomized to: a) RPL544 1.5 mg / RPL544 6.0 mg/Placebo, b) RPL544 1.5 mg / Placebo / RPL544 6.0 mg, c) RPL544 6.0 mg / RPL544 1.5 mg / Placebo, d) RPL544 6.0 mg / RPL544 1.5 mg, e) Placebo / RPL544 1.5 mg / RPL544 6.0 mg and f) Placebo / RPL544 6.0 mg / RPL544 1.5 mg, with the ratio of patients to treatment groups / treatment sequences being 1:1:1:1:1:1.

Patients will be screened for eligibility, including a reversibility test with salbutamol (in UK) or albuterol (in US) and ipratropium between 7 and 14 days before the first dose of study treatment. Eligible patients will then attend 3 separate treatment periods (Treatment periods 1 to 3), with each lasting 3 days and separated by a 7 to 14-day washout period. Figure 1 below summarizes these details.

Document: Z:\RPL554\UYA25849\Biostatistics\Documentation\SAP\Verona RPL554-CO-204 SAP v1.0

Author: [name] Version Number: 1.0

[figure not shown]
Version Date: [18OCT2018]

Template No.: CS_TP_BS016 Revision 5 Reference: CS_WI_BS005

Effective Date: 01Apr2018

Figure 1 Study Flow Chart

3.2. SCHEDULE OF EVENTS

Schedule of events can be found in Section 6 of the protocol.

3.3. CHANGES TO ANALYSIS FROM PROTOCOL

Not applicable.

4. PLANNED ANALYSES

There are no data monitoring committee (DMC) or interim analyses to be performed for this study. Only a final

Document: Z:\RPL554\UYA25849\Biostatistics\Documentation\SAP\Verona RPL554-CO-204 SAP v1.0

Author: [name] Version Number: 1.0

Version Date: [18OCT2018]

Template No.: CS_TP_BS016 Revision 5 Reference: CS_WI_BS005

Effective Date: 01Apr2018

Page 13 of 50

analysis will be performed.

4.1. DATA MONITORING COMMITTEE (DMC)

There will be no DMC analyses for this study.

4.2. Interim Analysis

No formal interim analysis is planned for the study.

4.3. FINAL ANALYSIS

All final, planned analyses identified in this SAP will be performed by IQVIA Biostatistics following Database Lock on a clean database:

- All outstanding data issues and queries resolved.
- All irresolvable data issues documented in the Data Handling Report (DHR) from Data Management.
- All coding of medications and AEs completed.
- Serious adverse event (SAE) reconciliation completed.
- All reconciliation of vendor data with electronic case report form (eCRF) data completed successfully.
- Analysis sets authorized.

It should be noted that all verbatim text from the eCRF will be presented in outputs "as is" with no "manual hard coding" corrections for such data.

PK analysis will be performed by another party (third party vendor), however details of this analysis will be specified in this SAP.

Document: Z:\ RPL554\UYA25849\Biostatistics\Documentation\SAP\Verona RPL554-CO-204 SAP v1.0

Author: [name] Version Number: 1.0

Version Date: [18OCT2018]

Template No.: CS_TP_BS016 Revision 5 Reference: CS_WI_BS005

Effective Date: 01Apr2018

5. ANALYSIS SETS

Agreement and authorization of patients included/excluded from each analysis set will be conducted prior to the unblinding of the study.

5.1. ALL SUBJECTS ENROLLED SET [ENR]

The all subjects enrolled (ENR) set will contain all subjects who provide informed consent for this study.

5.2. ALL PATIENTS RANDOMIZED SET [RND]

The all patients randomized (RND) set will contain all patients who provide informed consent and who are randomized to study medication. For analyses and displays based on RND, patients will be classified according to randomized treatment.

5.3. SAFETY ANALYSIS SET [SAF]

The safety analysis set (SAF) will contain all patients in the RND set who receive at least 1 dose of study medication and patients will be classified according to treatment received. If there is any doubt whether a patient was treated or not, they will be assumed treated for the purposes of analysis.

5.4. FULL ANALYSIS SET [FAS]

The full analysis set (FAS) will contain all patients in the RND set with sufficient data collected after intake of study medication to compute the pharmacodynamic parameters (FEV₁, sG_{aw}, RV, FRC measurements) on at least 2 treatment periods. For analyses and displays based on FAS, patients will be classified according to actual treatment.

Document: Z:\RPL554\UYA25849\Biostatistics\Documentation\SAP\Verona RPL554-CO-204 SAP v1.0

Author: [name] Version Number: 1.0

Version Date: [18OCT2018]

Template No.: CS_TP_BS016 Revision 5 Reference: CS_WI_BS005

Effective Date: 01Apr2018

Page 15 of 50

5.5. COMPLETERS ANALYSIS SET [CAS]

The completers analysis set (CAS) will contain all patients in the SAF analysis set who complete all treatment periods i.e., a patient who receives a first and last dose intake plus 1 day for all 3 treatment periods per schedule of events (see section 6 of the protocol for schedule details).

5.6. PHARMACOKINETICS [PK] ANALYSIS SET

The PK analysis set will contain all patients in the RND analysis set who have a blood sampling performed after at least 1 dose of RPL544 and PK parameter data. The PK analysis set will be determined by a third-party vendor and the data will be provided to IQVIA.

6. GENERAL CONSIDERATIONS

6.1. REFERENCE START DATE AND STUDY DAY

Study day will be calculated from the reference start date, and will be used to show start/stop day of assessments and events. Reference start date is defined as the day of the first dose of study medication (e.g., treatment period 1, Day 1 is the day of the first dose of study medication in treatment period 1), and will appear in every listing where an assessment date or event date appears.

If the date of the event is on or after the reference date then:

• Study day = (date of event - reference date) + 1.

If the date of the event is prior to the reference date then:

• Study day = (date of event – reference date).

Document: Z:\RPL554\UYA25849\Biostatistics\Documentation\SAP\Verona RPL554-CO-204 SAP v1.0

Author: [name] Version Number: 1.0

Version Date: [18OCT2018]

Template No.: CS_TP_BS016 Revision 5 Reference: CS_WI_BS005

Effective Date: 01Apr2018

Page 16 of 50

In the situation where the event date is partial or missing, the date will appear partial or missing in the listings, and study day, and any corresponding durations will be presented based on the imputations specified in Appendix 2; Partial Date Conventions.

6.2. BASELINE

Baseline definitions are related to the treatment period the patient enters. For majority of endpoints (primary endpoint, relevant secondary/exploratory endpoints and safety endpoints assessed post-dose in the treatment periods), this will be the pre-dose assessment on Day 1 of each treatment period (treatment period 1 to treatment period 3). Baseline pre-dose FEV₁/FVC will be derived from 3 acceptable readings (performed up to 8 times to obtain these), with the highest being used for analysis. For safety laboratory tests (hematology, biochemistry, urinalysis) and 24-hour Holter monitoring screening assessment, performed 7 to 14 days before randomization, will be considered as baseline.

6.3. REPEAT/RESCHEDULE, UNSCHEDULED VISITS AND EARLY TERMINATION DATA

In general, for by-visit summaries, data recorded at the nominal visit will be presented. If a visit is repeated/rescheduled due to variability in FEV₁ or other reason, the repeated/rescheduled visit, will be listed and summarized as the valid visit (same visit number assigned), at the discretion of the Investigator. Unscheduled measurements will not be included in by-visit summaries, but will contribute to the endpoint value, at the discretion of the Investigator. For example, if an unscheduled visit occurred at 10 hours post-dose on Day 3, then this value will be considered in the calculation of the average FEV₁ over 12 hours (AUC_{0-12h} FEV₁) on Day 3. Any unscheduled or unplanned readings will be presented within the patient listings.

Early termination data will be mapped according to the visit number the termination occurred for by-visit summaries. If early termination occurs pre-first dose (after baseline), then it is summarized at the actual visit. If

Document: Z:\RPL554\UYA25849\Biostatistics\Documentation\SAP\Verona RPL554-CO-204 SAP v1.0

Author: [name] Version Number: 1.0

Version Date: [18OCT2018]

Template No.: CS_TP_BS016 Revision 5 Reference: CS_WI_BS005

Effective Date: 01Apr2018

Page 17 of 50

termination is after first dose in period or during the following wash-out period, data collected remains at the visit performed. However, if the patient returns for end of study, then this data will be mapped to end of study visit.

If AE data occurs in the 7 to 14-day gap between treatment periods, these will be mapped to the earlier of the two treatment periods. Similarly, the AE will be mapped to the last treatment group received. If AE data occurs in the post-treatment period, these will be mapped to the last treatment period and last treatment group received.

Listings will include scheduled, unscheduled, repeat/reschedule and early discontinuation data.

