3.3 Planned Duration of the Study

The approximate planned duration for each patient could be up to 61 days: 7 to 14 days screening, up to 9 days treatment (three treatment periods of 3 days each separated by 7 to 14 days) and an end of study visit 4 to 10 days after the last treatment visit (Day 4 of Treatment Period 3). Repeat, rescheduled and unscheduled visits are permitted at the discretion of the Investigator.

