5.8 Blinding

Tiotropium/olodaterol will be used in trade dress and will not be blinded.

RPL554 and placebo will be administered double blind. The placebo is the same as the active medication (RPL554) except for the omission of the active ingredient. Because a visually matching placebo could not be developed, the dosing cup on each nebulizer administered at the study center will be obscured with opaque tape to visually blind the study medication.

The study personnel pouring the RPL554 and placebo into the nebulizer will therefore not be blinded to the study medication identity. This individual needs to be separate from other study center staff participating in the study, and may not reveal the appearance of the nebulizer contents to the patient or the blinded study staff. To ensure proper blinding, the Sponsor, Investigator (defined as Principal Investigator and all study physicians), all patients and all other research personnel (except bioanalytical personnel performing the pharmacokinetic assays and the unblinded study staff) will therefore be blinded to the treatment allocation.

The blind should be broken only if specific emergency treatment would be dictated by knowing the treatment status of the patient. If the blind needs to be broken, the Investigator should contact the Sponsor as soon as feasible. The Investigator may unblind the investigational product immediately if he/she feels it is necessary prior to contacting the Sponsor. However, the Investigator should promptly document and explain to the Sponsor any premature unblinding. Otherwise, all blinding will be maintained until all queries are resolved and the database is locked. Blind break envelopes will be provided to the site and must be kept in a secure access area.

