6 STUDY PROCEDURES AT EACH VISIT

The study will consist of the following:

- Screening will take place in the period between 7 and 14 days prior to the first study treatment administration. Screening procedures may be performed as a single visit or more than one visit. Since the Holter monitor is to be removed after 24 hours, patients will return one day after placement.
- Three treatment periods, each 3 days in duration and separated by 7 to 14 days (from last dose of study medication on Day 3 of each treatment period)
- An end of study visit between 4 and 10 days after the completion of Treatment Period 3 Eligible patients may be re-screened at the discretion of the Investigator.

Repeat, rescheduled, and unscheduled visits and procedures are permitted at the discretion of the Investigator.

The overall schedule of assessments at each visit is shown in Table 3 and the schedule of assessments on each day of each treatment period is shown in Table 4. Assessments are listed by visit in Section 1.1 to Section 6.4 and are described in Section 7.

Post-dose assessments should be performed in the following order: 1) ECG, 2) vital signs, 3) pharmacokinetic blood sample, 4) spirometry (prioritized on the timepoint).

Verona Pharma plc CONFIDENTIAL Page 30 of 66

Table 3 Overall Schedule of Assessments at Each Visit in RPL554-CO-204

Procedures	Screening	(7 to	End of Study			
Frocedures	14 to 7 days before Randomization	Day 1	Day 2	Day 3	Day 4	4 – 10 days after Day 4 o Treatment Period 3
Informed consent	X					
Demographics including height and weight	X					
Medical/surgical and disease history	X					
Eligibility criteria	X	X[a]				
Physical examination	X (Full)	X (Brief)			X (Brief)	X (Full)
Vital signs	X	X	X	X	X	X
Safety laboratory tests: hematology and biochemistry	X				X	X
Safety laboratory tests: urinalysis	X					X
Viral serology	X					
Alcohol breath test	X					
Serum pregnancy test (females of childbearing potential)	X					
Urine pregnancy test (females of childbearing potential)	X	X				X
Chest X-ray (or in last 12 months)	X					
12-lead ECG	X	X	X	X	X	X
24-hour Holter monitoring	X			X		
Spirometry: Reversibility test	X					
Spirometry: Study measurements		X	X	X	X	X
Whole body plethysmography training	X					
Whole body plethysmography		X		X		
Inhalation training (nebulizer and Respimat®)	X	X				
Randomization		X[a]				
Tiotropium/olodaterol and RPL554 or placebo dosing		X	X	X		
Pharmacokinetic sampling				X		
Dyspnea scale		X		X	X	

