9.4.8 Handling of Withdrawals or Missing Data

Patients withdrawn after only one treatment period will not be included in the efficacy analyses. Imputation of data for calculation of average (AUC) effects for FEV₁ will be described in the statistical analysis plan. No other imputation of missing data will be performed.

All available data from all dosed patients who have received study treatment will be listed and summarized. Any unscheduled or unplanned readings will be presented within the patient listings, but only the scheduled readings will be used in any summaries. If a visit is rescheduled due to variability in FEV₁ or other reason, the rescheduled visit will be listed and summarized as the valid visit.

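### Does leaving unscheduled FEV1 readings to the Investigator's discretion put the endpoints at risk?

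*SAP*

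**What the plan says.** On unscheduled readings SAP 6.3 states: "Unscheduled measurements will not be included in by-visit summaries, but will contribute to the endpoint value, at the discretion of the Investigator". Its illustration concerns the Day 3 12-hour endpoint: "if an unscheduled visit occurred at 10 hours post-dose on Day 3, then this value will be considered in the calculation of the average". The sentence before it uses the same phrase for rescheduled visits, which "will be listed and summarized as the valid visit (same visit number assigned), at the discretion of the Investigator".

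The protocol uses the phrase for a different decision, namely whether an extra visit or procedure takes place. Section 6 says "Repeat, rescheduled, and unscheduled visits and procedures are permitted at the discretion of the Investigator", and section 3.3 says "Repeat, rescheduled and unscheduled visits are permitted at the discretion of the Investigator".

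Protocol 9.4.8 lists unscheduled readings, "but only the scheduled readings will be used in any summaries". The same section leaves one FEV1 matter to the SAP: "Imputation of data for calculation of average (AUC) effects".

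On safeguards, protocol 5.8 says that, apart from emergency unblinding, "all blinding will be maintained until all queries are resolved and the database is locked". Protocol 9.2 has the pre-lock meeting decide whether patients, or particular data from a patient, are left out.

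**The concern.** The wording of SAP 6.3 points two ways. Its verbs suggest that any extra reading goes in, while the reference to discretion suggests that someone chooses. On the second reading nothing in 6.3 stops the choice from depending on the value itself, and no decision time or record is required. Two programmers could derive different averages from the same data. The sentence also speaks of the endpoint value in general and offers the 12-hour average only as an example, so the primary peak FEV1 might be exposed too. Finally, it sits awkwardly beside protocol 9.4.8, while SAP 3.3 declares no change from the protocol. At stake would be an endpoint open to selection after the value is known.

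**Working it through.** **Which endpoints are open.** SAP 15.2.1.2 computes AUC by trapezoid on actual times and does not restrict it to scheduled points, so an extra reading can enter the Day 1 average over 12 h and the Day 3 averages over 4, 8, 12 and 24 h. Trough, onset of action and the evening peak have named times in SAP 15.2.1. For the morning peak, SAP 15.1.1 lists seven times (5, 15 and 30 minutes; 1, 1.5, 2 and 4 h). SAP 6.6 and protocol 9.4.5 speak only of the largest reading in the four hours. The Day 1 peak refers to 15.1.3, which has no list of its own. The specific list would normally govern, but no text says so, and both cases are checked below.

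**Inputs.** Spirometry times are from protocol 7.2.1. The 70 patients, the 1.3 L baseline and the difference of about 50 mL are from protocol 9.5. Three inputs are assumptions that the documents do not give:
- an extra reading lies d = 100 mL off the line between its neighbours (range 50 to 200);
- under chance variation, d has mean 0 and SD 100 mL (range 50 to 200);
- 1 or 7 of 70 patients have one such reading in a given treatment.

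The plan states no figure on this point to reproduce.

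**AUC endpoints.** A reading placed midway in a gap of g hours changes the average over T hours by (g/2)/T × d. If only readings above the line are kept, the expected change is (g/2)/T × SD/√(2π), and 100/√(2π) = 39.9 mL. The table uses the widest gap within each interval.

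| Average over | Gap | Weight | d = 100 mL: patient | 7 of 70 | Selective, SD 100: patient | 7 of 70 |
|---|---|---|---|---|---|---|
| 4 h | 2 to 4 h | (2/2)/4 = 0.250 | 25.0 mL | 2.50 mL | 9.97 mL | 1.00 mL |
| 8 h | 2 to 4 h (also 4 to 6 and 6 to 8 h) | (2/2)/8 = 0.125 | 12.5 mL | 1.25 mL | 4.99 mL | 0.50 mL |
| 12 h | 8 to 12 h | (4/2)/12 = 0.167 | 16.7 mL | 1.67 mL | 6.65 mL | 0.66 mL |
| 24 h | 16 to 23 h | (7/2)/24 = 0.146 | 14.6 mL | 1.46 mL | 5.82 mL | 0.58 mL |

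With 1 of 70 patients, the 12-hour figures are 16.7/70 = 0.24 mL and 6.65/70 = 0.09 mL. All entries halve at 50 mL and double at 200 mL. Including every reading has an expected shift of 0. The largest selective entry, 1.00 mL, is 1.00/1300 = 0.08% of the planning baseline and 1.00/50 = 2% of the planning difference.

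**Peak, if SAP 6.6 governed.** Suppose readings are independent and normal. Going from seven readings to eight raises the expected maximum from 1.352 to 1.424 SD, or about 0.071 SD. With an assumed reading-to-reading SD of 3%, 6% or 10% of 1.3 L, this is 2.8, 5.6 or 9.3 mL per affected patient and period. For 7 of 70 patients the treatment mean moves 0.28, 0.56 or 0.93 mL. Keeping only high readings adds nothing to this, because a maximum already ignores low ones.

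**The case for a change.** The strongest case for acting is that SAP 6.3 attaches discretion to entering the endpoint, not to ordering the visit, and that one sentence would settle it. That reading of the grammar stands, and so does the absence of a criterion.

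A second argument is that extra readings may be prompted by symptoms and so cluster in one treatment. Blinding does not prevent that. The bound is in the table: if 7 of 70 patients in one treatment only each had a reading 100 mL off in the same direction, the difference in the 4-hour average would move 2.5 mL (1.25 to 5.0), and in the 12-hour average 1.7 mL (0.83 to 3.3). Such readings would also be genuine measurements.

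A third argument concerns the primary endpoint. If SAP 6.6 governed, a reading 100 mL above all seven scheduled ones would raise that patient's peak by the full 100 mL, or 100/70 = 1.4 mL in the treatment mean. Seven such patients would give 10 mL. That is an extreme case: by symmetry, only one in eight extra readings drawn like the others would exceed the seven at all. It also requires setting aside the explicit list in SAP 15.1.1.

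The argument from protocol 9.4.8 does not carry far. That section speaks of summaries, which need not cover endpoint derivation. The SAP is also based on protocol version 2.0, whereas the supplied protocol describes itself as the first version, so no departure can be shown.

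A tighter rule can also do harm. Letting a late reading stand in for a missed one at its actual time would turn the 4-hour average into one over nearly 6 hours, because SAP 15.2.1.2 divides by the actual time of the last assessment.

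**Conclusion.** SAP 6.3 leaves a detail unstated, but results from the plan as written remain sound. The trapezoid on actual times takes an extra valid reading without bias in expectation. The peak, trough and onset definitions have named times to rely on. Whoever makes a choice does so blinded, and protocol 9.2 provides a meeting before lock at which particular data can be considered. Selection made without knowledge of treatment should act similarly on all three treatments and largely cancel in the comparisons. SAP 7.4 tests each secondary endpoint nominally, so no confirmatory claim rests on the averages.

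With selective inclusion in 7 of 70 patients at an SD of 100 mL, a treatment mean moves 0.50 to 1.0 mL depending on the interval, and at most 2.0 mL at an SD of 200 mL. These sizes rest on the assumed departures and frequencies, since the documents give neither. They would matter only if extra readings were far more common, or far more unequal between treatments, than assumed here. The gap is one that analysts fill sensibly, and closing it in the text would bring no material gain.
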